6.2.1.4 Sensitivity Analyses

A tipping point analysis allowing the handling of missing data in the two study arms to vary independently to determine thresholds where there is no longer evidence of a difference in the primary endpoint will be conducted. The analysis population will be the mITT population.

6.2.1.5 Supportive and Supplemental Analyses

The primary analysis will be repeated using the PP population. The strategies considered for handling intercurrent events will be the same in this analysis as for the primary analysis in the mITT population.

A supportive analysis will be performed on the primary endpoint using a logistic regression analysis model with treatment group and continuous covariates of age at baseline and number of co-morbidities at baseline included in the model as covariates. Parameter estimates, odds ratio and the corresponding 95% CIs will be provided. The strategies for handling intercurrent events will be the same in this analysis as for the primary analysis, and the population for analysis will be the mITT population.

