	
INB03 vs. Placebo. The primary endpoint treatment comparison will be evaluated using a one-sided $\alpha=0.005$ significance level. The odds ratio and corresponding 95% confidence intervals will be provided.
 
A supportive analysis will be performed using logistic regression with treatment and covariates of age and co-morbidities at baseline included in the model. Additional covariates may be added to the model and defined in the SAP.
 
Sensitivity and supplementary analyses will also be performed and are described in the protocol.
 
Binary secondary endpoints will be analyzed similarly to the primary endpoint using a CMH test, and continuous secondary endpoints, such as length of hospital-stay and change from baseline in inflammatory markers, will be analyzed using an analysis of covariance (ANCOVA) model and will include treatment and covariates such as age and number of co-morbidities.
 
Exploratory endpoints will be summarized by treatment group and may be analyzed similarly as the primary and secondary endpoints. Analysis of interview data collected on a subset of participants will be summarized in a separate report.
 
Interim Analysis:
 
An interim analysis will be performed when approximately 70 participants who meet the mITT population definition and have completed the Study Day 28 visit or who had an intercurrent event prior to Day 28. In order to maintain study blind, an independent unblinded statistical team will perform the analyses and present the results to the data monitoring committee (DMC).
 
The primary efficacy endpoint will be analyzed and a limited number of individuals who are not involved in the study conduct or review of day-to-day activities of the study will be informed on the unblinded efficacy results in order to plan further development and inform on other corporate objectives.
 
The DMC will also review unblinded safety and the primary efficacy data and recommend to the sponsor their unbiased opinion concerning safety and efficacy of INB03 in an acute COVID population.
 
Safety Analysis:
 
Safety data including AEs, vital sign measurements, ECGs, clinical laboratory information, and concomitant medications will be summarized descriptively for the safety population by treatment arm and overall. The safety set is defined as all randomized participants who have received any amount of study drug. AEs will be coded using the Medical Dictionary for Regulated Activities (MedDRA) classification system and summarized by System Organ Class and Preferred Term. For parameters measured over time, absolute values and changes from baseline will be summarized for each time point.

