4 STUDY DESIGN AND ENDPOINTS

4.1 Description of the Study Design

The trial is a Phase 2, double-blind, placebo-controlled, randomized clinical trial of INB03 in participants with pulmonary complications from COVID-19 infection. Each participant will complete up to 6 study visits.

Screening: Participants with a diagnosis of COVID-19 will be screened for study eligibility. Prior to any trial related procedures, participants will provide their consent to participate in the clinical trial. Screening assessments will include:

- collection of medical history/participant demographic (including race and ethnicity);
- physical examination (including vital signs, height and weight);
- room air oxygen saturation (SaO₂), if possible;
- chest imaging;
- ECG;
- WHO Ordinal Scale for Clinical Improvement (to be completed any time after informed consent is obtained and up to 1-hour post-randomization on Day 1);
- clinical laboratory evaluations (as per [Table 2: Clinical Laboratory Evaluations](#));

CONFIDENTIAL

- serum or urine pregnancy test for women of childbearing potential (WCBP).

If any of the above assessments are performed as part of routine clinical care within 1 day of Screening, they do not need to be repeated.

Study Day 1: Eligible participants will be randomized to receive either INB03 at 1mg/kg by subcutaneous injection (SC) + standard of care (SOC) or Placebo SC injection + SOC within 1 day of Screening. Participants will receive their first dose of study drug after randomization. Blood samples to check TNF levels and perform an anti-drug antibody test will be collected before dosing. Clinical assessments while participants are inpatients will be as per routine management of hospitalized COVID-19 patients including daily collection of vital signs, physical exam, concomitant medications and laboratory evaluations. 12-lead ECGs and chest imaging assessments will be performed if deemed clinically necessary. Additionally, use of non-mechanical ventilation will be collected daily until the participant is discharged from hospital.

The WHO Ordinal Scale will also be completed daily until the participant is discharged from hospital.

The sponsor recognizes that SOC may change over time. The study protocol allows therapies that have shown benefit in well-designed prospective randomized trials. Each clinical site can select their SOC.

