6.4.3 Randomisation

Participants will be randomized 1:1 on Study Day 1 in a blinded fashion to either treatment with INB03 or Placebo. Due to the complexity of COVID-19 and need for immediate randomization, each site pharmacist will be provided with a randomization schedule unique to the specific site. Separate randomization schedules will be generated for each site participating in the trial. The same criteria for generation of the list will be used for each site (e.g., block size, list structure) but lists will be unique for each site. The pharmacist at each site will be unblinded and will be responsible for providing the randomization number to site personnel.

An independent unblinded statistical team will generate each unblinded randomization schedule and will provide each list directly to the site pharmacist in a secure manner.

Full details of the randomization process, roles and responsibilities, will be described in the Pharmacy Manual.

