7.2.2 WHO Ordinal Scale for Clinical Improvement

The Ordinal Scale for Clinical Improvement is from the WHO R&D Blueprint designed for use in the COVID-19 population to measure illness severity over time. The scale will be completed for all participants at Screening (any time after consent is obtained and up to 1-hour post-randomization at Day 1). Daily assessments will be conducted using the Ordinal Scale for Clinical Improvement while participants are inpatients during the afternoon hospital rounds until participants are discharged from hospital.

The scale will also be completed at the time of hospital discharge, at the Day 28 follow-up visit and a final assessment with the Ordinal Scale for Clinical Improvement will be conducted on the Day 40 final safety visit.

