5.5 Pooling of Sites

Sites will be pooled for all analyses.

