6.2.1.2 Primary Analysis

The primary endpoint is binary in nature and will be analyzed using a stratified Cochran-Mantel-Haenszel (CMH) test. Stratification factors of Age (≤ 50 , >50 to 65, >65) and number of comorbidities (1, 2, 3+) will be included to compare the response rate of INB03 + SOC to Placebo + SOC. Treatment differences, odds ratios (ratio of odds in INB03 + SOC arm to the odds in Placebo + SOC only arm) and the 95% confidence interval will be provided. If expected cells counts are not sufficient for each strata, strata levels will be combined for the analysis as follows:

- Age will be split by the median in the mITT population (ie: $<$ median, \geq median)
- 1-2 comorbidities vs. 3+ comorbidities

If still not sufficient, a non-stratified Chi-square analysis will be conducted instead of CMH.

The number and percentage of patients with disease progression by Day 28 will be summarized by treatment arm.

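### No planned analysis of the primary endpoint adjusts for baseline respiratory severity, which is recorded for every participant, or for site, the only stated factor that separates the allocation lists

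*SAP*

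**What the plan says.** **Primary test.** SAP 6.2.1.2 specifies a CMH test: "Stratification factors of Age (≤ 50 , >50 to 65, >65) and number of comorbidities (1, 2, 3+) will be included". If cells are too sparse, age is split at the median and the co-morbidity count is reduced to two levels. The last step is: "If still not sufficient, a non-stratified Chi-square analysis will be conducted instead of CMH".

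**Supportive model.** SAP 6.2.1.5 specifies a logistic regression with "treatment group and continuous covariates of age at baseline and number of co-morbidities at baseline included in the model as covariates". Protocol 9.5.1.1 has the same terms. The protocol synopsis, under Statistical Methods, left room for more: "Additional covariates may be added to the model and defined in the SAP". The SAP adds none.

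**Severity data.** Protocol 7.2.2 says of the WHO ordinal scale: "The scale will be completed for all participants at Screening". SAP 6.2.2.1 uses a baseline WHO value as a covariate only when change in that scale is itself the outcome.

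**Site.** Protocol 6.4.3: "Separate randomization schedules will be generated for each site participating in the trial". Neither document states any other stratification of the randomisation. Protocol 4.1 adds: "Each clinical site can select their SOC". SAP 5.5 then says: "Sites will be pooled for all analyses".

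**The concern.** The endpoint is a step up in respiratory support, or death. How much support a participant needs at entry is therefore an obvious candidate predictor. Hospitalised participants can enter at WHO level 4 (no oxygen), 5 (mask or prongs) or 6 (NIV or high flow), and exclusion criterion 2 removes those in immediate need of intubation, CPAP or BIPAP. None of this reaches the primary or supportive analysis. The two adjusters that are used also overlap, because age 65 or over is itself one of the counted co-morbidities (Protocol 5.1).

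Allocation was not stratified by severity and only 77 participants were dosed (SAP 6.2.4), so chance imbalance is a practical matter. At stake is whether a reader who sees unequal baseline severity has a prespecified estimate that allows for it, or only one chosen after unblinding. SAP 6.2.4 sends unblinded primary results to selected sponsor staff to plan development, which makes prespecification worth having.

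Site is the lesser part. Lists are separate by site and sites choose their own standard of care, yet no analysis reflects this.

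**Working it through.** **1. The plan's own figure.** Inputs from SAP 3.3: 21% against 7%, one-sided alpha 0.005, power 90%. With unpooled variance, n per arm = (2.576 + 1.282)² × (0.21×0.79 + 0.07×0.93) / 0.14² = 14.88 × 0.2310 / 0.0196 = 175.4, so 176 against the stated 173. Power at 173 per arm is 89.5%. The figure reproduces to within 2%. It uses an unadjusted test and does not depend on this point.

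**2. Events at the achieved size.** With 77/2 = 38.5 per arm, expected events are 38.5 × (0.21 + 0.07) = 10.8. That averages 10.8/18 = 0.6 per arm per stratum with nine strata, and 10.8/8 = 1.35 with four. The SAP gives no threshold for sufficient cells. Under the common minimum of 5 (an assumption), both steps fail and the primary test becomes the unstratified chi-square. The supportive logistic model is then the only adjusted analysis of the primary endpoint in the mITT population.

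**3. Chance imbalance.** The documents give no severity mix, so prevalence is assumed. The table gives the hypergeometric probability that a binary severity category differs between arms by 10 points or more.

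| Assumed prevalence | 39 vs 38 | 173 vs 173 |
|---|---|---|
| 15% | 22% | not computed |
| 20% | 25% | 1.5% |
| 30% | 32% | 4.6% |
| 50% | 37% | 5.3% |

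If the number in the 15% category is itself left random, the first figure is 23%.

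**4. What such an imbalance does.** Assume 25/60/15% at WHO 4/5/6, with placebo risks of 8/20/47%.
- Overall risk: 0.25×8 + 0.60×20 + 0.15×47 = 21.05%, which matches the planned 21%.
- Average risk at levels 4 and 5: (2 + 12)/0.85 = 16.5%.
- Shift from a 10-point excess at level 6: 0.10 × (47 − 16.5) = 3.05 points.
- Standard error with 38.5 per arm: √(0.2310/38.5) = 7.7 points at the planned rates, or √(2×0.21×0.79/38.5) = 9.3 points if both arms are at 21%.
- The shift is therefore 3.05/9.3 = 0.33 to 3.05/7.7 = 0.39 standard errors.

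Over repeated randomisations on these assumptions, case mix alone moves the expected difference by 3 points or more in 27% and by 5 points or more in 7%.

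**5. Power.** CMH was simulated at one-sided 0.005 with 15 sites, blocks of 4, a binary severity factor at 30%, and no age or co-morbidity strata (4,000 runs per row). All of these are assumptions.

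| N | Severity OR | Site SD (logit) | Unadjusted | By severity | By site |
|---|---|---|---|---|---|
| 346 | 3 | 0 | 89.9% | 91.0% | 90.0% |
| 346 | 5 | 0 | 89.6% | 92.2% | 89.7% |
| 346 | 3 | 0.5 | 89.7% | 90.6% | 90.2% |
| 346 | 5 | 0.7 | 89.0% | 91.5% | 89.8% |
| 77 | 3 | 0 | 18.1% | 18.8% | 16.7% |
| 77 | 5 | 0 | 18.6% | 21.2% | 17.6% |
| 77 | 3 | 0.5 | 18.4% | 19.4% | 18.3% |
| 77 | 5 | 0.7 | 18.4% | 19.6% | 18.7% |

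A second simulation at N = 346 used the step 4 mix and compared age × co-morbidity strata with WHO strata. Power was 84.0% against 88.5%, 82.2% against 85.5% with site effects, and 84.5% against 85.8% under a milder gradient. Site strata gave 84.2% against 82.2%. Crossing site with severity at N = 77 cut power to about 11%, through sparse strata.

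**6. Type I error.** At N = 346 with site effects (10,000 runs), rejection under the null was 0.0045 to 0.0046 unadjusted, 0.0044 to 0.0047 by severity and 0.0049 to 0.0053 by site. The Monte Carlo standard error is √(0.005×0.995/10,000) = 0.0007. No null run was made at N = 77.

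**The case against.** The protocol makes extra covariates optional, so a SAP that adds none contradicts nothing. That stands: this is an improvement, not an inconsistency.

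A reader might infer that an imbalance in severity would go unseen. The documents do not support that. SAP 6.2.2.1 presents WHO values by arm, and SAP 6.3.6.3 reports room-air SaO2 at screening. What is missing is an estimate that corrects for the imbalance.

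A reader might also infer that the test is invalid because site is ignored, or that imbalance could by itself produce the result. Step 6 shows no inflation, and any effect of ignoring within-site balance is slightly conservative. Step 4 puts a 10-point imbalance at about 3 points, against a planned effect of 14.

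The power gains are small, rest on assumptions, and are largest at a sample size the trial will not reach. That stands too. Nor should the 82% to 84% levels in the second simulation be set against the planned 90%: applying an odds ratio of 0.283 within its severity levels gives an INB03 rate of 7.6%, not 7%. Only the differences within that simulation are informative.

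Two objections bear on the remedy. The Screening score may be recorded up to an hour after randomisation, while Protocol 6.3 has dosing immediately on randomisation, so some scores may follow the first dose. And WHO level 6 includes NIV, which overlaps the CPAP and BIPAP component of the endpoint. Both are right and have to be met in the wording.

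**Conclusion.** The point holds as one of precision and interpretability. Severity recorded on every participant, and the one stated factor separating the allocation lists, are both absent from every planned analysis of the primary endpoint. (Full randomisation details are in the Pharmacy Manual, which is not among the documents.)

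The size is modest. At 77 dosed, an imbalance of 10 points or more has a probability of about 22% to 37% for assumed prevalences of 15% to 50%. Its effect, under the assumed risks, is about 3 points or 0.3 to 0.4 standard errors. Adjusting for severity gains roughly 1 to 5 points of power at N = 346, and about 1 to 2.5 points at N = 77 in the scenarios where severity is prognostic. Site gives no material gain at N = 77 (from −1.3 to +0.3 points). The case rests on having a prespecified adjusted estimate in a small trial, not on power.

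**What to change.** Amend the SAP before the preliminary unblinded analysis. SAP section 1 provides for amendment before final lock and unblinding.

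- **SAP 6.2.1.5:** add baseline WHO score to the supportive logistic model. Define it as the last score before first dose, in line with SAP 5.2. Enter it as one linear term, or as categories at the cost of two parameters. Use Firth penalisation, given about 11 expected events.
- **Same section:** state how a baseline score of 6 is handled, since NIV overlaps the endpoint.
- **Optional:** add a supportive site-stratified CMH as a check of consistency with the design, and reword SAP 5.5 so that sites are pooled except in that analysis. Do not cross site with severity.

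The primary CMH and its alpha stay as they are. The cost is SAP wording and one or two output rows. The downside is one or two more parameters with few events, and little information from small sites; a site with only one arm contributes none.

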6.2.2 Secondary Efficacy Endpoints and Analyses

Secondary efficacy endpoints will be analyzed for patients included in the mITT population. No adjustment for multiplicity is planned therefore nominal p-values will be provided for secondary endpoints. All data on the secondary endpoints will be provided in data listings.

6.2.2.1 Continuous Endpoints

Descriptive statistics will be provided for each endpoint and will be reported by treatment arm. Endpoints that are not normally distributed will also display geometric means. Absolute values and changes from baseline will be presented for the following:

- Inflammation markers (COVID-19 Specific markers: eGRF, Troponin, CRP, Ferritin, D-dimer)
- WHO Ordinal Scale for Clinical Improvement

Baseline will be defined as the value in the database prior to receiving any amount of study treatment. Line plots of means with error bars for the above endpoints will be presented by treatment group. Figures of means for both absolute values at each timepoint and the changes from baseline will be provided.

Changes from baseline will further be analyzed statistically using a mixed model repeated measures (MMRM) analysis. Factors include treatment arm, timepoint, age (≤ 50 , >50 to 65 , >65) and number of co-morbidities (1, 2, 3+). The baseline value of the endpoint will be included as the covariate. Patient will be repeated by timepoint. An unstructured covariance and the Kenward Roger's approximation for the degrees of freedom will be assumed. Least-square means will be provided for the treatment differences (INB03 + SofC vs Placebo + SofC) as well as the corresponding 95% CIs.

Descriptive statistics will be provided for the following endpoints and reported by treatment arm.

- Length of stay in index hospital
- Days to disease progression

Length of stay in index hospital will be derived as the index hospital discharge date – randomization date +1. Time will be considered in the derivation if collected for both dates. If discharge date is missing, date of death or end of study date will be used, whichever comes first.

Days to disease progression is not a specified secondary endpoint in the clinical study protocol, however is of interest to summarize. Days to disease progression will be derived as the first date of disease progression – randomization date +1. Intercurrent events, as defined in Section 6.2.1.3, will be considered when assigning a patient as having disease progression. Patients with no disease progression and who have completed the study will be censored as the duration on study. Patients who terminated the study early and with no disease progression according to Section 6.2.1.3 will be censored and given the longest duration, 40 days.

A multi-factor analysis of variance (ANOVA) will be used to assess the differences between treatment arms for each endpoint. Treatment arm, age (≤ 50 , >50 to 65 , >65) and number of co-morbidities (1, 2, 3+) will be included as factors in the model. Least-square means will be provided for the treatment differences (INB03 + SofC vs Placebo + SofC) as well as the corresponding 95% CIs. If assumptions for ANOVA are not met then a comparable non-parametric test will be performed (e.g., rank ANOVA or Wilcoxon rank-sum tests).

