4.2.2 Secondary Endpoints

The secondary endpoints of the study are:

- Proportion of participants with all-cause mortality;
- Proportion of participants who transfer to ICU level care by Day 28 (ICU level care is defined as a hospital setting where patient to nurse ratio is < 4);
- Proportion of participants with a new onset of neurologic disease (requiring medical intervention), including stroke by Day 28;
- Proportion of participants with evidence of new CHF or new MI requiring medical intervention by Day 28;
- Proportion of participants with a new onset embolus or thrombus by Day 28;
- Proportion of participants who develop a need for renal replacement therapy (defined as need for any type of dialysis including intermittent or continuous peritoneal or hemodialysis) by Day 28;
- Proportion of participants with an increase in the WHO Ordinal Scale of Clinical Improvement score at any time during the study;
- Length of hospital stay defined as the number of days in hospital from time of randomization to time of discharge or death, whichever occurs first;
- Change from baseline in inflammation markers over time.

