5.4 Handling of Withdrawal or Termination

Participants withdrawing from the study will be encouraged to complete the same final evaluations as participants completing the study according to this protocol (Day 40 assessments).

Reasonable efforts will be made to contact participants who are lost to follow-up. Investigator will be expected to try as much as possible to re-connect those participants at the end of the trial in order to obtain at least their vital status. These efforts must be documented in the participant's file.

Investigators will be trained about the importance of participant retention and steps to prevent missing data.

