6.2.1.3 Handling Missing Data

The following intercurrent events may lead to missing data for the primary endpoint. Imputation will be performed when the primary endpoint of mechanical ventilation or death information prior to Day 28 is missing.

Intercurrent Event	Strategy	Method of handling missing data
Withdraw consent prior to Day 28	While on treatment – data prior to event is of interest	the last available post-randomization record of the WHO Ordinal Scale for Clinical Improvement, prior to the intercurrent event, will be used to assess disease progression
Lost to Follow-up prior to Day 28 with no hospital discharge date	Composite variable – event is considered informative about patient's outcome	the participant will be considered to have disease progression
Lost to Follow-up prior to Day 28 with a hospital discharge date	Treatment policy – data is used as if event never occurred	the last available post-randomization record of the WHO Ordinal Scale for Clinical Improvement, prior to the intercurrent event, will be used to assess disease progression
Discontinued from study for reasons other than Withdrawal of consent or Lost to Follow-up prior to Day 28	Treatment policy – data is used as if event never occurred	the last available post-randomization record of the WHO Ordinal Scale for Clinical Improvement, prior to the intercurrent event, will be used to assess disease progression
Did not receive mechanical ventilation due to unavailability	Hypothetical – data is used assuming event did not occur	the last available post-randomization record of the WHO Ordinal Scale for Clinical Improvement, prior to the intercurrent event, will be used to assess disease progression

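### Length of stay: if the end of study date is the exit date, an inpatient who leaves the study early is analysed as a completed short stay

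*SAP*

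**What the plan says.** Protocol 4.2.2 defines the endpoint: "Length of hospital stay defined as the number of days in hospital from time of randomization to time of discharge or death, whichever occurs first". Leaving the study is not one of the endings.

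SAP 6.2.2.1 gives the derivation: "Length of stay in index hospital will be derived as the index hospital discharge date – randomization date +1". For a missing discharge date it adds: "If discharge date is missing, date of death or end of study date will be used, whichever comes first". The analysis follows: "A multi-factor analysis of variance (ANOVA) will be used to assess the differences between treatment arms for each endpoint". The fallback is also uncensored: "If assumptions for ANOVA are not met then a comparable non-parametric test will be performed".

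Two other rules bear on the same participant:

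- SAP 6.2.1.3 has a row for "Lost to Follow-up prior to Day 28 with no hospital discharge date". When the primary outcome is missing, "the participant will be considered to have disease progression". Withdrawal of consent has its own row and is scored from the last WHO ordinal value.
- For days to progression, SAP 6.2.2.1 censors early terminators without progression and gives them the longest duration, 40 days.

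Protocol 9.5.2 leaves intercurrent-event handling for each secondary estimand to the SAP. SAP 6.2.2.2 names a strategy for the binary endpoints. None is named for length of stay, so the missing-date sentence is the only handling.

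**The concern.** For someone who leaves the study alive while still an inpatient, neither discharge nor death has been observed. The true stay is at least as long as the time to exit. The rule nevertheless closes the stay, and the model cannot tell it from a real discharge on that day. Ranking does not help, because an early exit still ranks among the short stays.

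The error has a direction: a short stay is the favourable result, so the arm that loses more inpatients looks better. The treatment of the participant is also inconsistent. A person lost to follow-up in hospital can count as a failure in the primary analysis and as a short stay here, while the days-to-progression rule in the same section gives early terminators the longest duration.

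Length of stay is a named secondary objective, and SAP 6.2.4 reports only 77 dosed participants, so a handful of exits carries weight.

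**Working it through.** The documents state no mean, SD, expected effect or number of in-hospital exits for length of stay. There is no figure to reproduce, and every size below rests on stated assumptions.

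**1. One participant.** Take randomization on Study Day 1 and apply end date − randomization date + 1.

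| Participant | End date used | Recorded stay |
|---|---|---|
| Discharged on Day 3 | Day 3 | 3 − 1 + 1 = 3 days |
| Leaves study on Day 3, still inpatient; end of study = exit date | Day 3 | 3 days |
| Same person; end of study = a later date such as Day 40 | Day 40 | 40 days |

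The undefined term therefore decides whether the person has one of the shortest stays or one of the longest.

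**2. Shift in an arm mean.** With k such exits among n participants, true stay T and exit day E, the mean falls by k × (T − E) / n. Take n = 38, since 77 dosed gives about 38 per arm if split evenly.

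| E | T | One exit | Three exits |
|---|---|---|---|
| 3 | 14 | 11/38 = 0.29 | 33/38 = 0.87 |
| 3 | 28 | 25/38 = 0.66 | 75/38 = 1.97 |
| 3 | 40 | 37/38 = 0.97 | 111/38 = 2.92 |
| 5 | 14 | 9/38 = 0.24 | 27/38 = 0.71 |
| 5 | 28 | 23/38 = 0.61 | 69/38 = 1.82 |
| 5 | 40 | 35/38 = 0.92 | 105/38 = 2.76 |

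**3. Against sampling error.** The assumed model is 38 against 39 participants, no true effect, and lognormal stays (median 6 days, log-SD 0.8, capped at 28, mean 8.4). Leavers are drawn from those with true stays over 7 days and exit on Days 2 to 4. In 5,000 simulated trials:

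- The standard error of the difference between arms is about 1.4 days.
- Three exits in one arm shift the difference by about 0.87 days, and 0.87 / 1.4 ≈ 0.6 standard errors.
- The false-positive rate of a two-sided t-test rises from 4.8% to 9.9% at the 5% level, and from 0.9% to 2.4% at the 1% level that SAP 5.1 sets by default.

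A harsher choice makes the leavers the three longest stayers in one arm (lognormal, mean 8, SD 6, capped at 40, exit on Days 2 to 5). The difference then moves from −0.02 to −1.51 days.

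**4. Equal losses.** In that second model, with three such exits in each arm, the difference is −0.04 days before the rule is applied and −0.05 after. The bias depends on imbalance in the exits.

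**The case against.** The strongest reply is that little of this is demonstrated.

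- **The end of study date is undefined.** SAP 5.2 uses the term without saying what it is, and SAP 5.3 gives an imputation only for interim or ongoing reporting. Protocol 5.4 encourages withdrawers to complete the Day 40 evaluations and asks sites to re-contact lost participants "in order to obtain at least their vital status". For a lost participant the date might be the last contact or something later. This stands, so the point is conditional. The ambiguity itself still needs settling.
- **A death date might be overridden.** A reader might infer that the earlier-date rule discards known deaths. That requires a death date found after exit and an end of study date not updated to match it. It is a possible outcome of the wording, not an established one.
- **The clash with the primary score is narrow.** A reader might infer that every inpatient who leaves is counted as ventilated or dead in the primary analysis. Only loss to follow-up before Day 28, with no discharge date and missing outcome data, is scored that way automatically.
- **The size is assumed.** No exits are reported, and SAP 6.2.4 says participants randomized by the termination date were followed to completion, which suggests few. Nothing in the documents shows that leavers have longer stays than others. An exit on Day 15 would be recorded above the assumed mean of 8.4 days, though still understated.
- **The consequence is limited.** This is one of several secondary endpoints with nominal p-values, and the planned listings would let affected participants be found.

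None of this answers the core: a stay not known to have ended is entered as finished.

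**Conclusion.** The point holds in conditional form. Where the end of study date is the exit date, SAP 6.2.2.1 turns an unfinished stay into a completed, falsely short one. That departs from the protocol's definition and runs against the SAP's own handling of early exit elsewhere.

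Under the assumptions shown (38 per arm, true stay 14 days, exit on Day 3), each exit costs about 0.29 days. Three in one arm cost about 0.87 days, or about 0.6 standard errors. Longer true stays make it larger, and balanced losses make it roughly vanish.

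A reader might go further and say that a few exits could create or hide the whole treatment effect on stay. The documents do not support that. They state no expected effect and no exit count, and a shift of about 0.6 standard errors distorts an estimate without manufacturing a result. Nor do they show which arm would benefit. The primary test is not affected.

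**What to change.** Amend SAP 6.2.2.1 as follows:

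1. Define the end of study date, separately for withdrawal, loss to follow-up and completion.
2. Use a known date of death in preference to an earlier end of study date.
3. Do not treat the stay of a participant who left alive and still in hospital as completed. In the day-count or rank analysis, place these participants with the longest stays. This matches the 40-day rule for early terminators and, for loss to follow-up, the primary scoring in 6.2.1.3.
4. Report the number of such participants by arm.
5. As a sensitivity analysis, right-censor them at the last date known in hospital. Keep death as an end of stay, as the protocol defines it. Use few or no strata: three age groups by three comorbidity groups make nine strata for 77 participants. State that the censoring may be informative.

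The censored analysis should stay secondary, because the protocol specifies ANCOVA for this endpoint and censoring does not remove the bias if leavers differ from those who stay. The cost is SAP wording, a small programming change and a conservative assigned value for a few participants. No new data are needed. SAP Section 1 allows amendment before final database lock and unblinding.
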